## **14) Provisions to Monitor the Data to Ensure the Safety of Subjects**

**General Considerations:** The risks are greater than minimal risk (see section 17 for anticipated risks).

Every effort will be made to identify and address adverse events as they arise from the medication treatment. At each in person follow up visit, study staff will complete the side effects checklist with participants, monitoring for any changes in anticipated side effects; these side effects will be relayed to the study physician within 1 business day. The study physician will be allowed to decrease the dose, or discontinue the study medication as deemed necessary. Similarly, every effort will be made to address adverse events as they arise from the assessments including anxiety from exposure to affective or alcohol stimuli. If there are any serious adverse events we will take appropriate measures.

If a participant does experience excessive craving or anxiety as a result of the assessments, or neuropsychological testing, or expresses suicidal thoughts, [name] or covering medical provider will be available at any time to assess safety and make an attempt to help the patient. Although no aspects of the study are expected to be unduly upsetting or risky, established procedures are in place for the occurrence of such an emergency. Support will be available to deal with any anxiety, fatigue or increased urge to use alcohol associated with behavioral testing. There will a physician available any time by phone to talk with participants for any emergent medical adverse events from the medication. A standardized suicide risk assessment protocol is in-use by this team to assess for safety when participants report past or current suicidal thoughts, and [name] or covering medical provider will be called, and one of them will be available at any time to respond, if the protocol warrants their involvement.

Every effort will be made to protect the confidentiality of participants' records. However, complete confidentiality of records cannot be guaranteed as records may be examined by authorized personnel from the approving IRB, the FDA and MRN. Otherwise, records will be

kept strictly confidential and will not be inspected by any other agency unless required by law. Loss of confidentiality will be minimized by assigning a randomized number to each participant upon entry into the study. This number will be used for all correspondence between study investigators and all data collection and analysis after the initial screening visit. MRN has state-of-the art IT networks with all necessary security mechanisms in place for data storage. Any personal information entered into computers is password protected and monitored for suspicious activity. Moreover, all information will be in double-locked rooms per privacy specifications. The results of this research may be presented at meetings or in publications; however, participants' identity will not be disclosed.

Participants will be clearly informed of their right to withdraw from the study at any time and still receive full compensation for the time they participated.

There are no known health risks associated with the proposed MRI aspect of the study. A two-way intercom system and a video monitoring system provide continual monitoring of the participant's condition at all times. If discomfort or concern is expressed, or detected, the experiment will be stopped and the participant will be given the option to discontinue at any time. Absolute caution will be implemented to ensure that only non-ferrous objects are present during all of the MRI sessions. Participants will be asked to change into hospital scrubs prior to being placed in the scanner to ensure that they do not introduce any metallic objects into the imaging environment. Participants will also be screened for the presence of a pacemaker or any other metallic objects in their body, such as an aneurysm clip, ear implant, or nerve stimulator. Participants with these or other metallic devices will not be allowed to participate in any of the previously described studies. The MRI also makes loud 'drum' beating noises during the study. Headphones or earplugs are provided for protection.

**Data and Safety Monitoring Committee:** Data and Safety Monitoring Committee will be established comprising the PI, study physician, research coordinator, and an external physician reviewer who is not otherwise affiliated with the study and does not report directly or indirectly to the PI. This committee will meet quarterly to review data quality, recruitment and retention, and to review all serious or clinically significant adverse events. In addition, the committee will review safety data, and follow-up on any serious adverse event that appears to be study related. The DSMC members will be blinded for participants who are currently enrolled. For all SAE's, investigators will consider and discuss the need for unblinding, based on the nature of the SAE, and based on whether or not knowing the group assignment would alter treatment of the SAE, within 48 hours. Patterns of adverse events as well as individual events may indicate the need for operational changes, protocol modifications, a decrease in dose, or, conceivably, discontinuation of the trial.

All side effects and adverse event information will be monitored for using a standardized checklist at all medication visits with the nurse or research coordinator. Study data will be reviewed quarterly, or more frequently as deemed necessary by the PI and study physician.

Adverse events (AEs) will be collected on an AE case report form when they come to the awareness of study staff. The form will include an assessment of clinical significance and study relatedness. AEs will be reported in accordance with federal law and policies and the IRB. Reporting procedures vary depending on the severity of the AE, and will follow the policies in the IRB manual. In particular, adverse events and other reportable events that are unanticipated and deemed related to research procedures and that result in greater risk of harm will be reported to the IRB within 7 days of discovery, regardless of whether they qualify as SAEs.

Serious Adverse Events: Adverse events (AEs), when present, will be collected on an AE case report form at the end of each drug administration session and at all subsequent visits. The form will include an assessment of clinical significance and study relatedness. Serious Adverse Events (SAEs) will be documented on a separate SAE form. SAEs will be reviewed by the Data and Safety Monitoring Committee at its quarterly meetings. These will also be reported to IRB within 48 hours.

## 15) Participant Complaints

If a participant wishes to issue a compliant or request information about the research, they may notify any study team member or the PI, [name], at [contact], Monday – Friday from 8am – 5pm. Participants may also contact the UNM Office of the IRB, [contact], [[contact]](mailto:[contact]). Website: <http://irb.unm.edu/>

Depending on the nature of the complaint, the problem will be resolved directly with the participant, if possible, in a confidential and timely manner. Complaints that constitute a reportable event will be submitted to the IRB within 7 days. Participant complaints will be coded with a unique research subject identifier (URSI) and kept in their respective study folder in a locked office for record-keeping purposes.

## 16) Withdrawal of Subjects

Participants may withdraw from the study at any time. All unused study medication can be returned to study staff who will return it to the pharmacist for proper disposal.

## 17) Risks to Subjects

Gemfibrozil: The risks of the medication are greater than minimal risk. There are three main safety concerns of gemfibrozil in adults: self limited transaminitis, gallstones and rhabdomyelisis. Our methods will allow us to explore for any adverse events in these and unexpected areas, and we will be aggressive about checking liver tests and following up concerning symptoms. We are also checking CK levels (for subclinical rhabdomyelisis) at baseline. To our knowledge there have been no clinical reports of the combinations of gemfibrozil and alcohol causing significant problems, and gemfibrozil is not contraindicated in individuals who also drink alcohol, although patients are warned about the risks of alcohol counteracting the triglyceride lowering effects in the package insert. Moderate amounts of alcohol co-administered with gemfibrozil in rats did not cause alterations in LFTs and authors concluded that a moderate amount of alcohol with gemfibrozil is safe in rats. Based on their association with gemfibrozil treatment in past work, stomach upset or pain, diarrhea, nausea, or vomiting will be monitored for using a standard checklist as well as symptoms of more serious side effects (right upper quadrant abdominal pain, nausea, vomiting would be concerning for gallstones; muscle aches or weakness, dark colored urine would be concerning for rhabdomyolisis). The FDA has determined this medication to be exempt from needing an IND (see attached IND exemption letter – gemfibrozilINDExempt.pdf).

MRI: Radio and magnetic waves associated with MRI scans are not associated with any known adverse effects. MRI is non-invasive and considered minimal risk by the FDA and OHRP. However, the scanner is a large magnet, so it could move objects containing ferrous metal in the room during the scan. All participants are screened using the MRI safety screening form prior to being scanned. Participants may be bothered by feelings of claustrophobia (uncommon). The MRI also makes loud ‘drum’ beating noises during the study. Headphones or earplugs are

provided for protection. Rarely, large or recent tattoos can heat up during an MRI scan and cause skin irritation like a sunburn (uncommon). No long-term harmful effects from MRI are known. However, since the effect of MRI on early development of the fetus is unknown, participants who are pregnant will not be allowed to go in the MRI. Females will be asked to take a urine pregnancy test before being allowed to participate in the study. The test results will only be shared with participant. All MRI sequences used are within FDA approved parameters, including specific absorption rate. Due to the very high sensitivity of MRI in detecting abnormalities, there is a risk of false-positive findings, identifying something on imaging studies that may or may not be important. This may result in anxiety and a referral for additional medical testing, possibly including a recommendation for clinical scans at the participant's cost.

**Blood drawing risks:** Drawing blood may cause temporary pain and discomfort from the needle stick, occasional bruising, sweating, feeling faint or lightheaded and in rare cases infection or nerve pain.

**General (uncommon) risks:** Participation in this study may result in discomfort, emotional stress, behavioral fatigue, and inconvenience.

**Privacy and Confidentiality:** Participation in this study may produce emotional stress, inconvenience or an invasion of privacy (uncommon). There is also a risk of breach of data confidentiality (uncommon).

There may also be side effects or risks to study participation that are unforeseen and not known at this time.

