### Exclusion Criteria

- 1) severe liver disease; severe kidney disease; gallbladder disease or gallstones
- 2) chronic renal or hepatic failure
- 3) recent pancreatitis
- 4) insulin-dependent diabetes
- 5) other urgent medical problems
- 6) moderately elevated liver function tests (AST or ALT greater than 2 times upper limit of normal) or elevated creatine kinase (CK)
- 7) schizophrenia, schizoaffective disorder, Bipolar I disorder, suicidal thoughts in the last month
- 8) current moderate or severe other substance use disorder (SUD; except nicotine or marijuana)
- 9) active legal problems with the potential to result in incarceration
- 10) pregnancy or lactation, or child bearing age and not on birth control or not willing to use other birth control methods (e.g. condoms)
- 11) current daily use of anti-craving medications, mood stabilizers, benzodiazepines, or anti-psychotics
- 12) regularly taking a medication contraindicated for use with gemfibrozil including other fibrates, statins, repaglinide, or which are believed to interact with gemfibrozil such as dasabuvir, dabrafenib, loperamide, montelukast, paclitaxel, pioglitazone, rosiglitazone, colestipol, colchicine and warfarin
- 13) a history of alcohol withdrawal-induced seizures or delirium tremens (hallucinations, disorientation) requiring hospital admission during the last ten years
- 14) a history of moderate or severe traumatic brain injury (TBI; loss of consciousness  $>30$  minutes)
- 15) left-handedness
- 16) any contraindications for MRI

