### Screening visit

After the participant has reviewed and signed the consent form, breath alcohol will be measured (<.01 required), participants will complete a 90 day timeline follow-back (TLFB) to establish adequate drinking levels for inclusion, a handedness questionnaire, and a MRI safety screener to assess eligibility. In addition, participants will be interviewed using portions of the Structured Clinical Interview (SCID) for Psychotic, Anxiety, Mood, and Drug and Alcohol Use Disorders to establish whether they have moderate to severe AUD and/or exclusionary SUD and psychiatric disorders. In addition, all participants will complete a urine drug screen and female participants will complete a urine pregnancy test. In addition, trained research staff will conduct a blood draw to obtain baseline levels of CBC, LFT's, BMP, triglycerides, GGT, and CK. Expected time: 2 hours

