### Medical history visit

If participants are eligible based on the screening visit, a subsequent visit will be scheduled for the study physician to conduct a physical examination and medical history. If not already completed at the screening visit (visit 1), trained research staff will conduct a blood draw to obtain baseline levels of CBC, LFT's, BMP, triglycerides, GGT, and CK. Expected time: 2 hours

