#### Intervention

Participants who meet study criteria will be randomized to active treatment or placebo. The placebo group will receive capsules (filled with microcrystalline cellulose powder) which look identical to capsules filled with active treatment, and will receive the same number of capsules as for active treatment. Members of the study team will be blinded to study randomization; the study pharmacist and/or another honest broker at MRN (e.g. member of the Research Operations team) will be un-blinded, and the pharmacist will not interact with any of the participants. Gemfibrozil will be prescribed at 600 mg by mouth twice daily, *which is the standard FDA approved dose used for the treatment of hypertriglyceridemia*. Adherence will be monitored with bi-weekly pill counts. At the first med dispensing visit (30 minutes, baseline), participants will receive basic information about possible side effects and will be provided with a 2-week supply. During the follow-up med dispensing visit at Visit 5 (15 minutes), individuals will undergo a review of side effects.

All individuals will also receive 4 sessions of motivational enhancement therapy (MET), thus reducing ethical concerns of non-treatment. Therapists will be trained by a MINT-trained trainer.

#### Visit 4

One week after starting medication, participants will complete the second MET session. In addition, participants will complete TLFB, PACS, Helping Alliance Questionnaire, and the CIWA. Expected time: 30 minutes

### Visit 5

Two weeks after starting medication, an additional two weeks of medication will be dispensed, the third MET session will take place, and a follow-up MRI scan (identical to baseline scanning session), blood draw, and assessments will take place. The blood draw will be used to measure LFT's, GGT, and triglyceride levels. Assessments will include the CIWA to measure withdrawal, the ICS to measure impaired control, the PACS to measure craving, the TLFB to measure drinking, the Helping Alliance Questionnaire, and medication side effects. Expected time: MET (30 minutes), MRI (1 hour), Med dispense (30 minutes), Assessments/blood draw (1.5 hours)

### Visit 6

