Four weeks after starting medication, the fourth MET session will take place as well as a blood draw and assessments. The blood draw will be used to measure assess LFT's, GGT, and triglyceride levels. Assessments will include the CIWA to measure withdrawal, the ICS to measure impaired control, the PACS to measure craving, the TLFB to measure drinking, the Helping Alliance Questionnaire, and medication side effects. Expected time: MET (30 minutes), Assessments/blood draw (2 hours)

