### Phone Call

Six weeks after starting medication, a phone assessment will be used to collect TLFB and PACS data and side effects/other symptoms that may be associated with terminating use of the medication. Expected time: 30 minutes

For all questionnaires listed above, participants may refuse to answer any question at any time. Direct identifiers will be collected and maintained in the MRN COINS database. All data collected as part of this study will be coded with a Unique Research Subject Identifier (URSI).

Instrument/Activity	Screen (Visit 1)	Screen (Visit 2)	Baseline (Visit 3)	Visit 4	Visit 5	Visit 6	Phone Call
Breathalyze	X		X		X		
SCID	X						
TLFB	X		X	X	X	X	X
MRI Screener	X		X		X		
Edinburgh Handedness	X						
Urine Drug Screen	X		X		X		
Pregnancy Test	X		X		X		
Exclusion Criteria List		X					
Medical History		X					
Physical Exam		X					
Blood draw		X			X	X	
PACS			X	X	X	X	X
ICS			X		X		
CIWA			X	X	X		
ADS			X				

FTND			X				
AUDIT			X				
WTAR			X				
DERS			X				
S-DERS			X				
ERQ			X				
PROMIS Anger			X				
PROMIS Depression			X				
PROMIS Anxiety			X				
MCQ			X				
Emotional WM			X				
Digit Span			X				
DRINC			X				
Helping alliance Questionnaire			X	X	X	X	
SoCRArTES			X				
Treatment Services Review			X				
Demographics			X				
Locator			X				
MRI			X		X		
Motivational Enhancement Therapy			X	X	X	X	
Medication Dispensing			X		X		
Medication Dosing Handout			X				
Medication Count				X	X	X	X
SAFETEE/Adverse events				X	X	X	X
Total time (hours)	2	2	4.5	.75	3.5	2.5	.5
Total Payment	\$20	\$20	\$60	\$10	\$80	\$50	\$10

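### Is measuring creatine kinase only before dosing at odds with the reason the protocol gives for measuring it?

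*Combined protocol and SAP*

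**What the plan says.** Section 17 (Risks to Subjects) names three main drug concerns: liver enzyme rises, gallstones and rhabdomyolysis. It says the study's methods allow adverse events in these areas to be explored, and the same sentence goes on to stress liver testing and pursuit of worrying symptoms. The next sentence reads: "We are also checking CK levels (for subclinical rhabdomyelisis) at baseline".

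The rest of the protocol treats CK as follows:

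- Exclusion criterion 6 in Section 6 bars people with "moderately elevated liver function tests (AST or ALT greater than 2 times upper limit of normal) or elevated creatine kinase (CK").
- The Screening visit in Section 10 obtains "baseline levels of CBC, LFT's, BMP, triglycerides, GGT, and CK". The Medical history visit is the fallback: "If not already completed at the screening visit (visit 1), trained research staff will conduct a blood draw to obtain baseline levels" of the same analytes.
- Capsules are first handed out later, at the Baseline visit (Visit 3).
- At Visit 5 (week 2), "The blood draw will be used to measure LFT's, GGT, and triglyceride levels". At Visit 6 (week 4), "The blood draw will be used to measure assess LFT's, GGT, and triglyceride levels". Neither list contains CK.

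The schedule table in Section 10 has a row "SAFETEE/Adverse events" marked at Visits 4, 5 and 6 and at the phone call. The call also asks about "side effects/other symptoms that may be associated with terminating use of the medication". Section 14 has side-effect reports passed to the study physician within one working day and lets that physician lower the dose or stop the drug.

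**The concern.** A value taken before the first capsule cannot show what the drug does. Section 17 mentions CK in its paragraph on gemfibrozil's risks and links it to the subclinical form of muscle injury, which by definition a symptom checklist will miss. A reader who takes the sentence as a promise to watch for silent muscle damage from the drug finds no scheduled test that could do so. Liver tests share exclusion criterion 6 with CK and are repeated twice on treatment. CK is not repeated, although blood is drawn at both visits.

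On that reading the stake is the safety of individual participants. The physician who may reduce or stop the drug would have only symptom reports to go on for muscle effects. Drinking, fMRI and triglyceride results would be unaffected.

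**Working it through.** The protocol gives no figure to reproduce here. The check is a count of panels, followed by a comparison of what the text says CK is for with when it is drawn and how it is used.

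**Count of scheduled blood draws**

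| Draw | Timing | Liver tests | CK |
|---|---|---|---|
| Visit 1, or Visit 2 if not yet done | before dosing | yes | yes |
| Visit 5 | week 2 | yes | no |
| Visit 6 | week 4 | yes | no |

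That is 1 + 2 = 3 draws. On treatment, liver tests are in 2 of 2 panels and CK in 0 of 2. The schedule table marks blood draws without naming analytes, so the visit descriptions decide the matter. The count behind the concern is right.

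**Symptom checks.** Visits 4, 5 and 6 plus the phone call make 4. Visits 4, 5 and 6 fall at weeks 1, 2 and 4, so 3 take place by the end of dosing.

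**Do purpose, timing and use agree?**

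1. *Timing.* Section 17 says baseline. The Screening and Medical history visits draw CK at baseline. Visits 5 and 6 leave it out. All of these agree.
2. *Use.* The only use stated for the result is exclusion criterion 6: a raised CK keeps the person out. That use is possible only with a value taken before dosing.
3. *Purpose.* Looking for subclinical muscle injury at baseline means looking for injury that is already present and silent. A test before dosing can find that, and criterion 6 acts on it. The purpose of showing a symptom-free effect of the drug is not in the sentence; a reader has to add it.
4. *The general assurance.* The statement that the methods allow adverse events to be explored is not left open. Its own sentence names liver tests and symptoms as the means. Later in the same paragraph Section 17 lists the muscle symptoms to be watched for: aching or weak muscles and dark urine. Gallstones, the third concern, are also followed through symptoms, so CK is not singled out.

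**Is any estimate lost?** No objective or endpoint uses CK. Nor would measuring it on treatment yield a useful rate. Section 9 closes enrollment at 20 randomized. If allocation is 1:1, which the protocol does not state, 20 / 2 = 10 receive the drug. If 70% of those complete two weeks, the low end of the Section 9 range, 0.70 × 10 = 7 remain. With no rises seen in n participants, the one-sided 95% upper bound is 1 − 0.05^(1/n):

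- n = 10: 1 − 0.05^(1/10) = 0.259, or 26%
- n = 7: 1 − 0.05^(1/7) = 0.348, or 35%

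The question is therefore one of individual safety monitoring. The plan's statistical content does not turn on it.

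**The case for a change.** The strongest argument for the concern comes from the protocol's own comparison of the two fibrates. Section 5 credits fenofibrate with the lower muscle risk and suggests that gemfibrozil may be easier on the liver. By that account muscle is where the chosen drug compares worse, yet the liver test is repeated and the muscle test is not, and no reason is given. A CK test prompted by symptoms, which nothing forbids, would still miss a rise without symptoms. Blood is already taken at Visits 5 and 6, so a further assay would need no extra needle stick.

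Part of this stands. No scheduled test would show a symptom-free CK rise during treatment, and the protocol does not explain why liver tests are repeated and CK is not. Section 17 could also say more plainly that CK is an entry screen.

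None of it makes the plan inconsistent. Giving no reason for a disclosed choice differs from stating one purpose and measuring for another. The documents do not say how often symptom-free rises occur over 4 weeks or whether they would call for action, so the benefit of repeating the test cannot be shown from them. Exclusion criterion 12 also bars regular use of statins, other fibrates and colchicine, among other drugs.

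**Conclusion.** The concern does not hold. CK is measured before dosing only, in 0 of 2 on-treatment panels, and that is what Section 17 says will happen. Stated purpose, timing and use fit together as a screen for silent muscle injury before the drug is started. Muscle effects during treatment are followed through symptoms, with three checks by the end of dosing and a fourth at the phone call.

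This rests on taking the words about baseline in Section 17 at face value and on reading its general assurance together with the methods named in the same sentence. What remains is a preference about safety monitoring, which is for the sponsor and the study physician to judge, or at most an optional clarification of wording. Neither would change an endpoint, an analysis or an estimate.

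### CK is measured only before the first dose, so no scheduled test can show a symptom-free rise on gemfibrozil; adding it to the week 2 and week 4 blood draws is a cheap, modest improvement

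*Combined protocol and SAP*

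**What the plan says.** Section 17 (Risks to Subjects) names transaminitis, gallstones and rhabdomyolysis as the leading safety issues with gemfibrozil in adults. It then says "Our methods will allow us to explore for any adverse events in these and unexpected areas", and the same sentence goes on to commit to close attention to liver tests and to pursuing symptoms that cause concern. On CK it says: "We are also checking CK levels (for subclinical rhabdomyelisis) at baseline". For muscle injury on drug it relies on a checklist, noting that "muscle aches or weakness, dark colored urine would be concerning for rhabdomyolisis".

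The laboratory schedule is in Section 10:

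- **Screening visit:** the panel is "baseline levels of CBC, LFT's, BMP, triglycerides, GGT, and CK".
- **Medical history visit:** the same panel, as a fallback: "If not already completed at the screening visit (visit 1), trained research staff will conduct a blood draw".
- **Visit 5 (week 2):** "The blood draw will be used to measure LFT's, GGT, and triglyceride levels". At this visit "an additional two weeks of medication will be dispensed".
- **Visit 6 (week 4):** the same three items as Visit 5.

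The schedule table at the end of Section 10 marks blood draws but lists no analytes. Exclusion criterion 6 bars people with raised CK and gives no numerical limit. Section 14 has side effects passed to the study physician within one business day and allows the physician to lower the dose or stop the drug.

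**The concern.** Section 17 gives the purpose of the CK test as finding subclinical rhabdomyolysis. A value taken before the first dose can screen out people whose CK is already raised, and it can serve as a reference. It cannot show a rise that develops on the drug. The checklist finds muscle injury that causes symptoms and, by its nature, misses a rise that does not. An unscheduled CK is possible at any time, but a symptom-free participant gives nobody a reason to order one.

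What is at stake is chiefly the safety of the individual. Criterion 6 removes raised CK at entry, so a raised value at Visit 5 would be new since screening, and it would appear with about half of the four-week exposure still to come. Efficacy analyses are not affected.

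**Working it through.** **Schedule.** The plan states no figure on this point, so the first step is to set the panels side by side.

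| Draw | Timing | CK included? | What a result could lead to |
|---|---|---|---|
| Screening or medical history visit | before drug | yes | exclusion under criterion 6; reference value |
| Visit 5 | week 2 | no | dose reduction or stopping, two weeks of drug remaining |
| Visit 6 | week 4 | no | follow-up only, as treatment is ending |

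Scheduled CK tests per participant: 1 before drug and 0 on drug, although blood is drawn twice on drug.

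**How many treated participants would give on-drug blood.** Section 9 closes enrolment at 20 randomised and expects about 70-80% to complete at least two weeks of medication. The allocation ratio is not stated; I assume 1:1, so 10 on gemfibrozil. Taking two-week completion as a stand-in for giving on-drug blood, n = 0.70 x 10 = 7 to 0.80 x 10 = 8. Section 26 speaks of 20 completers, which gives n = 10. Section 6 mentions N=40; if that many were randomised, n = 0.70 x 20 = 14 to 0.80 x 20 = 16.

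**Chance of seeing at least one raised value on gemfibrozil if CK were added.** Let p be the true proportion of treated participants who show a raised CK at a scheduled on-drug draw. The protocol gives no value, so 1%, 5% and 10% are assumptions. The chance is 1 - (1 - p)^n. For example, n = 7 and p = 0.05 gives 1 - 0.95^7 = 0.302.

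**What zero raised values would exclude.** The one-sided 95% upper bound is 1 - 0.05^(1/n). For n = 8 it is 1 - 0.05^(1/8) = 0.312.

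| n | p = 1% | p = 5% | p = 10% | Upper bound if none seen |
|---|---|---|---|---|
| 7 | 0.068 | 0.302 | 0.522 | 0.348 |
| 8 | 0.077 | 0.337 | 0.570 | 0.312 |
| 10 | 0.096 | 0.401 | 0.651 | 0.259 |
| 14 | 0.131 | 0.512 | - | 0.193 |
| 16 | 0.149 | 0.560 | - | 0.171 |

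Under the present schedule the chance of detection by a scheduled CK test is 0 in every row. With CK added and p = 1%, no raised value would be found 90-93% of the time for n = 7 to 10 (1 - 0.096 = 0.904; 1 - 0.068 = 0.932).

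**Assays.** 20 randomised x 2 draws = 40 at most. If 40 were randomised, 40 x 2 = 80.

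**The case against.** The strongest reply is that the plan has made a stated choice: laboratory monitoring for the liver and symptom follow-up for the rest, with the relevant muscle symptoms named. The CK test then reads coherently as an eligibility screen. Risk is also limited by design: statins, other fibrates, colchicine, severe kidney disease and raised CK are all excluded, and exposure lasts four weeks. Repeated transaminases might give an indirect and non-specific hint of muscle injury, although the protocol does not use them for that purpose. No passage gives a rate of symptom-free CK rise or shows that acting on one prevents harm.

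Most of this stands. It limits the point to a modest improvement but does not close the gap, because none of the existing cover prompts a CK test in someone without symptoms.

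Three stronger readings are tempting and are not supported:

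- **That the protocol contradicts itself.** Section 17 says the CK check is at baseline, and no section schedules or promises it later.
- **That a Visit 5 CK would inform the dispensing decision.** Draw and dispensing fall at the same visit, samples are processed at an outside laboratory (Section 22), and no turnaround time is given. The result may come back after the drug has gone home, so any action may have to be by later contact.
- **That a raised value would show drug injury, or that the trial could estimate a rate.** With a single pre-drug value in people who drink heavily, a new elevation in one participant cannot be attributed to drug. The placebo arm gives only a rough picture of background.

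**Conclusion.** The point holds as a modest safety improvement. It is certain from the documents that CK is scheduled only before drug and that two existing on-drug draws omit it. Whether the change would find anything is uncertain. With 7 to 8 treated participants giving blood, the chance of at least one raised value runs from 7-8% at an assumed 1% rate to 52-57% at 10%, and finding none would exclude only true rates above about 31-35%. These figures rest on 1:1 allocation, independence between participants, two-week completion as a proxy for giving blood, and assumed rates.

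The case therefore rests on the low burden of the test and the possibility of acting on a Visit 5 result, not on estimating how often CK rises. A reader might infer that muscle toxicity goes unmonitored on drug. That is not so: symptomatic injury is covered by the checklist, and only the symptom-free rise is missed.

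**What to change.** 1. Add CK to the assays on blood already drawn at Visit 5 (week 2) and Visit 6 (week 4). Visit 5 is the more useful; Visit 6 can only prompt follow-up.
2. Relay any value above the laboratory's upper limit of normal to the blinded study physician within one business day, extending the route that Section 14 already sets for side effects.
3. Let the physician decide on repeat testing, dose reduction or stopping, by contacting the participant after the visit if the result returns once drug has been dispensed.
4. Tabulate CK by arm against the pre-drug value, as descriptive data only.

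Cost: at most 40 assays for 20 randomised (80 if 40 were randomised), with no extra needle stick or visit; the protocol gives no assay price. Downside: some elevations unrelated to drug will need review under blinding, and the assays may well find no case.
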